9.4 Early Withdrawal of Subjects

9.4.1 When and How to Withdraw Subjects

Based on our current published [16] and unpublished clinical data, there were no subjects who needed to be withdrawn from the study prior to completion. The risks to the patients are expected to be minimal and akin to a standard apheresis procedure. The cells returned to the patients are autologous cells that will be treated (or educated) by CB-SCs.

In this study a patient may be withdrawn from this protocol at any points:

- 1) If they suffer some type of allergic or hypersensitivity reaction to the SCE treated cells precluding the infusion of the product.
- 2) If technical difficulties preclude the completion of apheresis.
- 3) If they do not want to complete the required post treatment follow-up testing.

Participation in this trial is VOLUNTARY for all subjects. If they choose not to participate, this will not affect their relationships with Hackensack University Medical Center or their rights to health care or other services to which they are otherwise entitled. If they decide to participate, patients are free to withdraw their consents and discontinue participation at any time without affecting their future care at Hackensack University Medical Center. In the event that a patient is withdrawn for above or any other unexpected reasons they will be allowed to continue to receive medical care for treatment associated problems.

9.4.2 Data Collection and Follow-up for Withdrawn Subjects

Even though subjects may be withdrawn prematurely from the study, it is imperative to collect toxicity data for 12 weeks after. We will use all possible methods (e.g. number of phone calls to subject, phone calls to health care proxy, if possible, certified letters, etc.) to confirm that the subject is truly lost for follow-up. If a patient withdraws from the study prior to their 12 month follow-up, enrollment of a replacement patient will occur.

10 Study Device

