8.2 Primary Study Endpoint

The primary study endpoint will be the occurrence of treatment-related adverse effects. Adverse events that occur during therapy (especially those that necessitate temporary or permanent discontinuation of therapy) and over the 12-month follow-up period will be assessed.

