12.2 Subject Population(s) for Analysis

All subjects who received treatment will be included in the safety analyses. The primary efficacy end point will be the change in C-peptide secretion between baseline and follow-up.

13 Safety and Adverse Events

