13.1.4 Adverse Event Reporting Period

The study period during which adverse events must be reported is normally defined as the period from the initiation of any study procedures to the end of the study treatment follow-up.

For this study, the study treatment follow-up is defined as 30 days following the administration of study treatment. Serious adverse events should be reported to the local IRB and FDA within 7-10 days from the time of the event. Minor events can be reported in an annual report

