13.1.7 Post-study Adverse Event

All unresolved adverse events should be followed by the investigator until the events are resolved, the subject is lost to follow-up, or the adverse event is otherwise explained. At the last scheduled visit, the investigator should instruct each subject to report any subsequent event(s) that the subject, or the subject's personal physician, believes might reasonably be related to participation in this study. The investigator should notify the study sponsor of any death or adverse event occurring at any time (during the 6-month follow-up) after a subject has discontinued or terminated study participation that may reasonably be related to this study. The sponsor should also be notified if the investigator should become aware of the development of cancer or of a congenital anomaly in a subsequently conceived offspring of a subject that has participated in this study.

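### The primary safety endpoint runs 12 months, but a treated patient withdrawn for declining tests need only be followed for toxicity for an unanchored 12 weeks, so the adverse-event rate can be biased downward

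*Combined protocol and SAP*

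**What the plan says.** Section 8.2 sets the endpoint: "The primary study endpoint will be the occurrence of treatment-related adverse effects". Adverse events during therapy and "over the 12-month follow-up period will be assessed".

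Section 9.4.1 opens its list of withdrawal grounds with "In this study a patient may be withdrawn from this protocol at any points". Items 1 and 2 concern a reaction that precludes the infusion and technical failure of apheresis. Item 3 is the ground that reaches a patient already infused: "If they do not want to complete the required post treatment follow-up testing".

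Section 9.4.2 says that after premature withdrawal "it is imperative to collect toxicity data for 12 weeks after". No starting point is given. It lists phone calls and letters as means of confirming that a subject is truly lost. It also has anyone who withdraws before the 12-month follow-up replaced.

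Section 12.2 states: "All subjects who received treatment will be included in the safety analyses". Section 12.1 reports treatment-related events as counts and percentages with exact binomial 95% intervals. Neither says how a patient observed for less than 12 months, or a replacement, is counted.

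Two other periods appear. Section 13.1.4 applies to every subject: "For this study, the study treatment follow-up is defined as 30 days following the administration of study treatment". Section 13.1.7 has the investigator notify the sponsor of "any death or adverse event occurring at any time (during the 6-month follow-up) after a subject has discontinued or terminated study participation", where the event may reasonably be related to the study.

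**The concern.** Treatment is a single infusion, so a patient who leaves afterwards has had the full exposure, and what is lost is observation. Refusing tests is foreseeable: the mixed meal test takes 180 minutes with nine sampling times and is repeated through follow-up. The protocol describes no status in which a patient stops those tests but remains under adverse-event contact to Month 12.

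A percentage over all treated patients in effect counts someone as event-free unless a related event has been seen. Missing part of the window can lower that percentage and cannot raise it. Patients who feel unwell or burdened may be more likely to decline tests, so the loss need not be random. With about 10 patients, one or two missed events would visibly change the primary result.

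**Working it through.** The plan states no expected adverse-event rate or interval width, so it has no figure of its own to reproduce here. The sample size of 10 is justified on C-peptide and does not bear on this point.

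**Length of the gap**

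Inputs: a 12-month window (8.2); 12 weeks = 84 days (9.4.2); one month = 365.25/12 = 30.44 days. Thus 84/30.44 = 2.76 months. Let *t* be the month of withdrawal, which is assumed.

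- Anchor at withdrawal: uncovered months = 12 − min(12, *t* + 2.76).
- Anchor at infusion: uncovered months = 12 − max(*t*, 2.76), since the patient is on study until *t* anyway.

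| Withdrawal at | 12 weeks from withdrawal | 12 weeks from infusion |
|---|---|---|
| just after infusion | 12 − 2.76 = 9.2 | 12 − 2.76 = 9.2 |
| Month 1 | 12 − 3.76 = 8.2 | 12 − 2.76 = 9.2 |
| Month 3 | 12 − 5.76 = 6.2 | 12 − 3 = 9.0 |
| Month 6 | 12 − 8.76 = 3.2 | 12 − 6 = 6.0 |
| Month 9 | 12 − 11.76 = 0.2 | 12 − 9 = 3.0 |

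With the anchor at withdrawal, the gap closes at 12 − 2.76 = Month 9.2. With the anchor at infusion, about 9.2 months are uncovered for anyone leaving before about Month 2.8, and some gap remains for any withdrawal before Month 12.

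**What other sections cover in that gap**

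- Section 13.2 requires possibly related serious events after the study period to be recorded and reported, with no time limit. It does not reach non-serious related events, which the endpoint includes.
- Section 13.2 also has the investigator ask about adverse events at each contact. No schedule of contacts is set for a withdrawn patient.
- Section 13.1.7 is a duty to notify the sponsor, not to collect data, and is limited to events that may be related. If its six months run from discontinuation, it reaches Month 7 for a Month 1 withdrawal (1 + 6) and Month 9 for a Month 3 withdrawal (3 + 6). If it means the Month 6 visit, it ends there. The text does not say which.
- The 30 days in 13.1.4 leave 1 − 30/365.25 = 92% of the 12 months outside the stated period, for every subject.

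**Effect on the reported rate**

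Assume *k* early withdrawals among the first 10 treated, *k* replacements who complete 12 months, and no observed event. Keeping all treated patients gives 0/(10 + *k*), with 10 fully followed. The exact upper 95% limit for 0/*n* is 1 − 0.025^(1/*n*).

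| *k* (assumed) | All treated | Upper limit | Followed 12 months | Upper limit | Rate if every withdrawn patient had an unseen event |
|---|---|---|---|---|---|
| 0 | 0/10 | 30.8% | 0/10 | 30.8% | 0/10 = 0% |
| 1 | 0/11 | 28.5% | 0/10 | 30.8% | 1/11 = 9.1% |
| 2 | 0/12 | 26.5% | 0/10 | 30.8% | 2/12 = 16.7% |
| 3 | 0/13 | 24.7% | 0/10 | 30.8% | 3/13 = 23.1% |

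Early loss followed by replacement therefore tightens the reported limit with no gain in the number observed for the full window.

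**The case against.** The other side has several fair points.

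- A reader might infer that withdrawn patients drop out of the primary safety endpoint. They do not: 12.1 and 12.2 keep all treated patients. The fault is incomplete ascertainment, not a smaller denominator.
- A reader might illustrate three withdrawals as 0/10 reported with only seven followed. That ignores the replacement rule in 9.4.2. With replacements who complete, 13 are treated and 10 are followed.
- A reader might treat 13.1.7 as a second collection window that competes with 9.4.2. It is a different duty, and because there is a Month 6 visit, its six months may refer to that visit. What stands is only that its anchor is unclear.
- Safeguards exist. Withdrawal under 9.4.1 is permitted, not required. Unresolved events are followed up (13.1.7), late possibly related serious events are reportable (13.2), and 9.4.2 does continue toxicity collection for a time. These narrow the gap. None provides active collection of new non-serious related events to Month 12.
- Section 9.4.1 says that no earlier subject needed to be withdrawn, so three withdrawals is an illustration, not a forecast. The direction of the bias does not depend on that number.

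**Conclusion.** The point holds as a mismatch between a 12-month primary endpoint and a shorter, unanchored requirement for withdrawn patients. It matters for withdrawal before about Month 9.2 if the 12 weeks run from withdrawal, and for any withdrawal before Month 12 if they run from infusion. The possible bias in the primary rate is downward. Its size depends on how many patients leave, when they leave, and whether they have related non-serious events afterwards; the documents give none of these.

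The 0/13 figure assumes three early withdrawals, three replacements who complete, and both groups counted. The last follows from 12.2 but is not spelled out, and 8.1 caps enrolment at 10 without mentioning replacements. The documents do not support saying that treated patients leave the analysis or that late related serious events would go unreported. The 30-day period in 13.1.4 is a separate conflict with 8.2; correcting it alone would leave 9.4.2 as it is.

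**What to change.** 1. In 9.4.1 item 3, treat refusal of tests as stopping those tests only. Adverse-event contact continues unless the patient withdraws consent to contact.
2. In 9.4.2, collect adverse events for every infused patient who still agrees to contact at least through Month 12 from infusion, or for 12 weeks after withdrawal if that ends later. Month 12 is a minimum, so late withdrawals lose no coverage.
3. Reconcile the 30-day period in 13.1.4 with the 12 months in 8.2. State the anchor of the six-month period in 13.1.7 without shortening that notification duty.
4. In 12.1 and 12.2, state that all treated patients, including those withdrawn and their replacements, are in the primary count. Report beside it the number followed for the full 12 months and the rate in those patients.

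The cost is a wording amendment and a few phone contacts per withdrawn patient, with no added procedure. Withdrawal of consent to contact can still end collection, so a complete 12 months cannot be guaranteed; item 4 makes any remaining gap visible.

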10.1 Description

To build upon previous clinical trials abroad [1-3] using a closed-loop system, we will investigate the use of the SCE as a static device, which will allow increased interaction time (14-17 hours) between CB-SCs and patient lymphocytes/monocytes under a controlled good manufacturing process (GMP) environment before reintroducing the lymphocytes back into the patient. The longer interaction between CB-SCs and lymphocytes/monocytes will improve treatment efficacy using this optimized discontinuous system. Through secreted and cell-surface signaling molecules, the CB-SCs educate the lymphocytes [1,5]. The cells returned to the patients are autologous cells that have been treated (or educated) by CB-SCs. CB-SCs remain inside of the device due to their unique attaching ability [1-3,5]. Additionally, in this clinical trial, we design a chamber (160 \times 160 \times 200 cm) for co-culture of lymphocytes and CB-SCs that includes twelve discs of the material with adherent CB-SCs sandwiched between a top cover plate and a bottom

collecting plate (**Figure 1**). The device is manufactured, assembled and packaged in a Class 100K clean room. After being sterilized by gamma-irradiation (Cesium-137), the devices are stored at the room temperature in dark cabinets of Class 100K clean room, which is FDA-approved facility for cell isolation and cultures. The materials used to produce the device are FDA-approved for *in vivo* use per the United States Pharmacopeia (i.e., Grade Class VI Plastic). The sterilized device is a single use, which CB-SCs are generated from one cord blood unit for one subject application.

10.2 Treatment Regimen

[figure not shown]
Subjects who meet all criteria will be scheduled for treatment. All enrolled subjects will receive treatment with the SCE system consisting of a single session of MNC collection by apheresis approximately 10 L ($\sim 10^{10}$ mononuclear cells) of blood will be processed on day -1. The MNC product will then be exposed over a 17-hour period of time to the SCE and on day 0 the product will be infused intravenously back to the patient. All treated subjects will receive a telephone follow-up assessment on Day +1 to monitor for acute adverse events. All treated subjects will attend a safety visit on Day $+7 \pm 1$ day. Follow-up visits will occur on 1st, 3rd, 6th, 9th, 12th, and 24th month (± 5 days) post-therapy. Subjects will be instructed to record daily insulin doses, sugar levels, and physical activities. After receiving the SCE therapy, patients' daily insulin doses will be monitored and adjusted by their own physician.

10.3 Method for Assigning Subjects to Treatment Group

There is only one treatment group. Based on fasting C-peptide levels (a by-product of insulin biosynthesis, with normal reference range 0.8 – 3.1 ng/mL), as an indicator for islet β cell function, all participants will be characterized and assigned as one group having moderate T1D with some residual β cell function (fasting C-peptide level ≥ 0.3 ng/mL, n = 10). Each participant will receive one treatment.

10.4 Preparation and Use of Study Device

To build upon previous clinical trials abroad [1-3] using a closed-loop system, we will investigate the use of the SCE as a static device, which will allow increased interaction time (at least 17 hours) between CB-SCs and patient lymphocytes/monocytes under a controlled good manufacturing process (GMP) environment before reintroducing the lymphocytes back into the patient. The longer interaction between CB-SCs and lymphocytes/monocytes will improve treatment efficacy using this optimized discontinuous system (**Figures 13 A and B**). Please see the Appendix 4 Master Batch Record (MBR) for the detailed information on the Preparation and Use of Study Device. Briefly, the whole procedure is outlined in the diagram (**Figure 4C**): 1) Preparation of SCE: A fresh donated human umbilical cord blood unit is received, and mononuclear cells are isolated using a Ficoll gradient separation followed by removal of remaining Red Blood Cells (RBCs) using lysis buffer. The entire mononuclear cell suspension is seeded in the SCE, and cultured for 10-20 days. Once the culture is $\geq 80\%$ confluent, the SCE is ready to use. 2) Preparation of SCE-treated MNC: The day after the culture is $\geq 80\%$ confluent, the recipient's MNC Apheresis is collected on day -1 and shipped to the GMP facility; the SCE is washed and the CB-SCs in the SCE are cocultured overnight with the recipient's MNC Apheresis product, which contains lymphocytes and monocytes. After incubation, the patient cells are drained into a product collection bag. After final QC testing and product release, the product is sent to the recipient for administration.

[figure not shown]

Figure 4. Outline the preparation and use of Educator device. (A) Show the procedure how to produce SCE in GMP facility. **(B)** Display the protocols on ex vivo treatment of MNC by overnight co-culture with CB-SCs in GMP facility. **(C)** The detailed process overview.

Following steps will be applied for the Preparation and Use of Study Device. The production of clinical-grade SCEs and associated protocol have been mirrored by two Performance Qualification (PQ) runs at the FDA-registered cGMP facility, as demonstrated by PQ Reports from NYBC (see Appendix 2).

Step 1: Collection of human cord blood units.

Human cord blood units derived from healthy donors will be provided by FDA-registered CORD:USE Cord Blood Bank Inc. All cord blood samples are screened for communicable disease as requested by regulatory agencies.

Step 2: Preparation of CB-SC in the device.

Prior to introducing CB-SCs into the device, cord blood mononuclear cells are isolated from fresh cord blood unit (at least 100 ml/unit) according to the following protocol:

- 1) Take 50ml tubes and put in holders: normally use 4 tubes;
- 2) Add HISTOPAQUE®-1077 to each tube at 20ml/tube to isolate the mononuclear cells;
- 3) Plant mononuclear cells in the SCE Device (Tianhe Stem Cell Biotechnologis Inc.) at 1×10^6 cells/ml, 25-30ml/dish in serum-free culture medium; if $> 20 \times 10^9$ CD3 positive cells are collected by the apheresis procedure, the collection may be divided between two SCE Devices for one treatment.
- 4) Incubate cells at 37°C, 8% CO₂ conditions for 10~20 days.
- 5) Cell observation: CB-SC are round and attach on the bottom of dishes. If cell density reaches the 80% of confluence, CB-SC can be prepared for clinical application.

Step 3: Test the CB-SC culture for endotoxin and Gram stain.

- 1) **Testing for endotoxin.** The supernatant from the culture of CB-SCs will be collected into 1.8 ml sterilized tubes. Endotoxin will be tested by using the Endosafe-PTS Portable Test System (Charles River, Charleston, SC) and Endosafe-Licensed PTS Endotoxin Cartridge (0.005 EU/mL sensitivity, Catalogue #: PTS20005F, Fisher Scientific). The standard endotoxin level will be < 0.5 EU/mL. Only the Educator apparatus that meets this standard can be used for the clinical trial.
- 2) **Gram stain.** The supernatant from the culture of CB-SCs will be collected into 1.8 ml sterilized tubes. Gram staining will be performed by using the Gram Stain kit (BD Diagnostic Systems, Sparks, MD). Only the Educator apparatus that is negatively stained can be used for the clinical trial.

Step 4: Preparation of SCE.

- 1) Sterilized the hood in a GMP facility for preparation of SCE;
- 2) Clean out side of device with 70% ethanol gauze and carefully remove all caps;
- 3) Discard all supernatants inside of device;
- 4) Add physiological saline to each layer at 20ml/layer, washing each layer and removing all floating cells and debris;
- 5) Additional wash with physiological saline (20ml/layer);
- 6) Remove the caps from the top and bottom, replace with Plastisol Horseshoe Y Connectors;

Step 5: Treatment of MNC with SCE therapy.

- 1) On day -1 patients will undergo a steady state MNC collection by apheresis, with an optimal goal of processing approximately 10 L (~1010 mononuclear cells) of blood. Apheresis may be stopped before the goal is reached based on tolerability and venous access. A femoral apheresis catheter may be placed for the duration of the procedure if venous access is found to be insufficient on the day of collection, despite the initial venous assessment. The femoral apheresis catheter will be removed approximately 1 hour after the collection as per institutional SOP. A minimum of 6 L processed will be required to continue on to the next phase. Plasma will be added to the collection bag at the end of apheresis to target a product volume of 250 mL. Labeling of the product will be done prior to disconnecting the product from the donor in accordance with the Blood and Marrow Transplant program labelling policy.
- 2) The product will be packaged, stored and picked up by New York Blood Center (NYBC) in accordance with the Blood and Marrow Transplant program SOPs.
- 3) Testing for stem cell markers CD45 and OCT3/4 by flow cytometry on the cellular product. To exclude the contamination of CB-SCs in the Final Product, we will perform the flow cytometry by double-staining with CB-SCs' markers CD45 and OCT3/4 (Figure 3D).
- 4) Testing for identity markers CD4⁺CD25⁺CD127^{Low/-} Tregs by flow cytometry on the cellular product. The isotype-matched IgG antibodies will be served as negative controls. The Fc Blocker (BD Pharmingen) will be applied to block non-specific staining.
- 5) Testing for potency markers CD4⁺CD45RO⁺CCR7⁺ central memory T (T_{CM}) cells, CD4⁺ICOS⁺,CD8⁺ICOS⁺ T cells by flow cytometry on the cellular product. The isotype-matched IgG

antibodies will be served as negative controls. The Fc Blocker (BD Pharmingen) will be applied to block non-specific staining.

- 6) Once at NYBC, the cellular product will be processed and treated by CB-SCs according to the SOPs in Master Batch Record (Appendix 4).
- 7) On day 0, the educated cellular product will be infused to the patient in accordance with the Blood and Marrow Transplant program cellular infusion SOP.

Step 6: Test the Final Product for cell viability, endotoxin, Gram stain, mycoplasma, and stem cell markers.

- 1) **Cell viability.** The sample from the CB-SC-treated MNCs will be collected into 1.8 ml sterilized tubes. The cell viability will be tested by the trypan blue-based exclusion assay. The mononuclear nuclear cell number will be tested by using the Automated Complete Blood Counts (CBC) Using the Beckman Coulter® AC-T DIFF™.
- 2) **Testing for endotoxin.** The sample from the CB-SC-treated MNCs will be collected into 1.8 ml sterilized tubes. Endotoxin will be tested by using the Endosafe-PTS Portable Test System (Charles River, Charleston, SC) and Endosafe-Licensed PTS Endotoxin Cartridge (0.005 EU/mL sensitivity, Fisher Scientific). The standard endotoxin level for the final product will be ≤ 5 EU/kg/hr according to FDA guidelines. Only the Final Product that meets this standard can be used for the clinical infusion.
- 3) **Gram stain.** The sample from the CB-SC-treated MNCs will be collected into 1.8 ml sterilized tubes. Gram staining will be performed by using the Gram Stain kit (BD Diagnostic Systems, Sparks, MD). Only the Educator apparatus that is negatively stained can be used for the clinical trial.
- 4) **Testing for mycoplasma and sterility.** The Sterility and contamination of mycoplasma in the sample from the CB-SC-treated MNCs can be tested and excluded by following methods: 1). Regular cell culture: Cell viability can be monitored under phase-contrast microscope to exclude the contamination of bacteria. 2). Real time PCR: The sample from the CB-SC-treated MNCs will be collected into 1.8 ml sterilized tubes for mycoplasma and 50 mL tubes (total 120 mL) for sterility tests by Eurofins (Lancaster, PA) in compliance with the requirements of the US FDA Good Laboratory Practice Regulations (21 CFR 58). 3). The Sterility Testing will be performed by using a Direct Inoculation Method at Eurofins Company.
- 5) **Testing for stem cell markers CD45 and OCT3/4 by flow cytometry.** To exclude the contamination of CB-SCs in the Final Product, we will perform the flow cytometry by double-staining with CB-SCs' markers CD45 and OCT3/4 (**Figure 3D**).
- 6) **Testing for stem cell markers CD45 and OCT3/4 by flow cytometry.** To exclude the contamination of CB-SCs in the Final Product, we will perform the flow cytometry by double-staining with CB-SCs' markers CD45 and OCT3/4 (**Figure 3D**). The isotype-matched IgG antibodies will be served as negative controls. The Fc Blocker (BD Pharmingen) will be applied to block non-specific staining.
- 7) **Testing for identity markers CD4⁺CD25⁺CD127^{Low/-} Tregs by flow cytometry.** The isotype-matched IgG antibodies will be served as negative controls. The Fc Blocker (BD Pharmingen) will be applied to block non-specific staining.
- 8) **Testing for potency markers CD4⁺CD45RO⁺CCR7⁺ central memory T (T_{CM}) cells, CD4⁺ICOS⁺,CD8⁺ICOS⁺ T cells by flow cytometry.** The isotype-matched IgG antibodies will be served as negative controls. The Fc Blocker (BD Pharmingen) will be applied to block non-specific staining.

